8.4 Demographics, Other Baseline Characteristics (other than efficacy and safety variables)

Descriptive statistics of demographic characteristics will include:

- Age, gender (male; female)
- Ethnicity (Hispanic or Latino; not Hispanic or Latino), race (American Indian or Alaska Native; Asian; Black or African American, Native Hawaiian or other Pacific Islander)
- Height (cm)
- Weight (kg)
- Body mass index (BMI)

These characteristics will be summarized using the appropriate descriptive statistics by treatment group and overall for the Low-Level FCT ITT, the ITT, the Low-Level All Randomized the All Randomized analysis sets.

Other Baseline characteristics listed in Section 5 will be summarized using the appropriate descriptive statistics by treatment group and overall for the Low-Level FCT ITT analysis set and for the ITT analysis set.

8.5 Study Drug Usage

The following analyses will be presented for the Low-Level FCT ITT analysis set, the ITT analysis set, the Low-Level FCT All Randomized analysis set and the All Randomized analysis set. For each treatment group compliance will be calculated at each visit as well as for the overall study.

The calculation for percentage of compliance is 100 times the number of sachets dispensed at the previous visit minus the number of sachets returned, divided by the days between visits times 3 (not including days after the last visit at which sachets were dispensed if the subject did not return after that last visit).

If a subject was dispensed sachets at a given visit and then did not return to the study, the dispensation information at this last visit will not be used in the calculation of number of sachets used.

Summary statistics for these variables will include the number of subjects, mean, standard deviation, median, minimum and maximum.

8.6 Efficacy Analyses

The Analyses described below will be performed on every ITT, All Randomized and PP analysis set. The Low-Level ITT analysis will be considered the primary analysis set.

8.6.1 Primary Efficacy Analysis

The primary efficacy endpoint is the change from Baseline (score at Screening Part 1) to Week 12 visit in the ABC Irritability/Agitation (ABC-I) in the Low Level FCT ITT population as defined in Section 3. Descriptive statistics of ABC-I and change from Baseline ABC-I will be presented at Week 12 for each treatment group. Mean change in Baseline ABC-I at Week 12 will be compared across treatment groups using a mixed model repeated measures (MMRM) model with terms for treatment, study center, visit, and the treatment by visit interaction. The model will also include Baseline ABC-I score as a covariate and subject will be a random effect. An unstructured covariance matrix will be used for the within-subject correlation. Kenward-Rogers' approximation will be used to estimate degrees of freedom. The SLICE option will be employed to examine differences across treatments at specific time points, with the focus being on the Week 12 change from Baseline. Two-sided 95% confidence intervals of the difference between treatment means of the primary endpoint will be constructed using MMRM model estimates for the mean. Tests of hypotheses will be two-sided and will be based on the contrasts between CM-AT and placebo within the MMRM model.

An assessment of treatment-by-study center interaction on the change from Baseline (score at Screening Part 1) to Week 12 ABC-I will be carried out using analysis of variance (ANOVA). Included in the ANOVA model will be main effects for treatment, investigative center and Baseline ABC-I and the treatment-by-center interaction effect. A 0.10 level of significance will be used to assess the interaction. A non-significant interaction or an interaction significant but only quantitative in nature will support the pooling of results across study centers for the final analysis. For the PP, ITT, and All Randomized analysis sets, a treatment-by-low-level status interaction will be assessed in a similar manner as the treatment-by-study center interaction.

If statistical significance, in favor of CM-AT, is shown on the primary efficacy endpoint (FCT \leq 12.6 U/g) in the Low-Level ITT analysis set, the study will be considered a success statistically.

For completeness, though not of primary interest, descriptive statistics of ABC-I and of the change from ABC-I will be presented at each visit, and treatment group comparison p-values on mean change from Baseline ABC-I to each visit will be calculated from the MMRM model discussed above.

Missing ABC-I Data: The primary analyses will be based on the MMRM model with available data discussed above. As a sensitivity analysis, the above analyses will be repeated where, first, multiple imputation using the monotone linear regression approach will be used to impute missing primary endpoint data at each visit via SAS PROC MI; included as covariates in the linear model will be age, sex, race, ABC Irritability measured at previous visits (including the randomization visit), Baseline FCT, and investigative center.

Ten complete datasets will be created (the linear regression approach to multiple imputation assumes monotone missing data pattern; if such a pattern does not exist, then prior to each of the 10 linear regression imputations, non-monotone missing ABC-I data will be imputed via the MCMC approach on ABC-I across visits to create a monotone missing data pattern). Once complete datasets are generated, the primary MMRM model will be applied to each of these datasets with the results will be combined into a single estimate of the treatment difference on the change from Baseline to each visit using SAS PROC MIANALYZE. The focus is on the treatment difference on the change from Baseline to the Week 12 ABC-I as the primary analysis.

As an additional tertiary sensitivity analysis, the Last-Observation Carried Forward (LOCF) method will be applied prior to carrying out the MMRM analysis. For subjects who prematurely withdrew, the last efficacy measurement obtained prior to premature withdrawal (even if the last measurement is the Baseline measurement or the measurement obtained at the randomization visit) will be carried forward to each visit following the withdrawal prior to carrying out the MMRM.

8.6.2 The secondary efficacy endpoint of ABC-L will be analyzed and compared between treatments in a similar manner as the primary endpoint. Again, the Low-Level FCT ITT analysis set is primary, but all ITT, All Randomized and PP analysis sets will be analyzed.

8.6.3 Exploratory Endpoints:

For continuous exploratory endpoints, treatments will be compared on change from Baseline in a similar manner as the primary endpoint at Week 12 and each Post-Baseline visit except for multiple imputation and assessment of treatment-by-study center interaction effects. For CGI-S, an endpoint for which there is no Baseline value, treatments will be compared in a similar manner as the primary endpoint on the CGI-S value itself (as opposed to a change from Baseline) without a Baseline value of the endpoint as a covariate. There will be no adjustment for multiple comparisons.

For dichotomous exploratory endpoints (stool test, weight gain/loss), no formal statistical hypothesis testing will be performed to compare the treatment groups on these results.

The number and percentage of subjects experiencing the dichotomous endpoint will be presented for each treatment group. For completeness, this analysis will be repeated for each visit.

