	h. Any other investigational drug or therapy, oncology drug, anti- helminthic, or anti-yeast drug
	i. Off-label medications
	10. Asthma, when medication (oral, inhaled, or injectable) is given on a daily basis or is necessary >3 times per week.
	11. Ongoing dietary restriction for allergy or other reasons except nut allergies (lactose-free allowable)
	12. Inability to ingest the study drug
	13. Inability to follow the prescribed dosing schedule
	14. Subjects who are likely to experience significant changes in their ongoing psychosocial or medical treatments for autism over the course of the trial (e.g., initiation of new behavioral therapy, initiation of new medication or alternative treatment). Minor changes in ongoing treatment (e.g., missed therapy sessions due to holiday/vacation; planned break in therapy due to school holidays) will not be considered significant.
	15. Use of any stimulant medication or other medication given for ADHD must be discontinued 5 days prior to entering the study (Vayarin requires a 30-day washout)
	16. Subjects taking an SSRI must be on a stable dose for a minimum of 30 days prior to entering the study.
	17. History of premature birth < 35 weeks gestation
	18. Prior history of stroke in utero, or other intrauterine insult
Additional Inclusion Criteria at Visit 1/Baseline for	The subject must meet the following additional inclusion criteria upon returning for Visit 1/Baseline in order to be randomized:
Randomization:	
 
The subject must have demonstrated IP compliance that is ≥50% during the 2-week blinded drug run-in period
 
Upon retest at Visit 1/Baseline, the subject's score on the ABC-I must have increased or decreased by less than 30%, and also must be ≥9
 
Subjects must continue to meet all inclusion/exclusion criteria
 

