## Statistical Considerations:

The sample size is based on (a) the primary efficacy variable of the change from baseline to week 12 for the Aberrant Behavior Checklist (ABC) subscale for Irritability; (b) the primary analysis set of low-level fecal chymotrypsin (FCT)  $\leq$  12.6 Units/gram randomized subjects; and (c) a 1:1 randomization scheme. Assuming a mean  $\pm$  standard deviation decrease in ABC Irritability from baseline to week 12 of  $3.7 \pm 7$  for CM-AT and  $0.6 \pm 5$  for Placebo, a sample size of 82 evaluable low-level subjects per treatment group yields 90% power to declare a statistically significant difference between treatments at a two-sided 0.05 level of significance. Assuming 15% premature withdrawal, 97 low-level subjects will be randomized. In order to achieve 97 randomized low-level subjects per group, a total of 162 subjects per group will be randomized (based on previous data indicating 60% of autistic children are low-level).

Primary analyses (assessing CM-AT vs. Placebo difference) on change from baseline to week 12 will be estimated from a Mixed Model Repeated Measures (MMRM) across all visits assuming the unstructured within-subject correlation structure. Included in the model will be the main effects of randomized treatment group, visit, baseline ABC irritability, study center and the treatment-by-visit interaction effect. Analyses with and without imputation for missing data will be performed.

If statistical significance, in favor of CM-AT, is shown on the primary efficacy endpoint in the primary analysis set of low-level randomized patients (FCT  $\leq$  12.6 Units/gram), the study will be considered to be a success statistically. The secondary efficacy variable is change from baseline to week 12 in ABC Lethargy/ Social Withdrawal (ABC-L) of low-level randomized patients (FCT  $\leq$  12.6 Units/gram).

As an exploratory analysis, the MMRM analyses will be repeated on the ABC-I and ABC-L for the non-low-level FCT randomized patients (FCT > 12.6 Units/gram)

As an additional exploratory analysis, the above MMRM analyses will be repeated on the ABC-I and ABC-L on all randomized patients in a similar manner as for the low-level randomized patients.

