STATISTICAL ANALYSIS PLAN Protocol ID:00103 / Autism

A Double Blind Randomized Placebo Controlled Study of CM-AT for the Treatment of Autism in Children With All Levels of Fecal Chymotrypsin

Document Date: 27 December 2017

Upload Date: 2 May 2021

STATISTICAL ANALYSIS PLAN Amendment 1

A Double Blind Randomized Placebo Controlled Study of CM-AT for the Treatment of Autism in Children with All Levels of Fecal Chymotrypsin

PROTOCOL No. 00103 Autism

Sponsor:

Curemark, LLC

Date:

December 27, 2017

Approvals (sign and date):

Curemark, LI

[name], Ch

[name], Statistician

TABLE OF CONTENTS

1.	Study Objectives	3
2.	Study Design	3
	Study Analysis Sets	
4.	Test product, Dose and Mode of Administration	6
5.	Demographics, Other Baseline Characteristics (other than efficacy and safety	
	variables), Study Drug Compliance	6
6.	Efficacy Variables	7
7.	Safety Parameters	9
8.	Statistical Methodology	10
9.	Interim Efficacy Analysis	18
10	. Software	19
Sc	oring of the Aberrant Behavior Checklist (ABC)	20

1. Study Objectives

To examine children with autism at all levels of fecal chymotrypsin using the Aberrant Behavior Checklist.

Endpoint (outcome) measurements to determine efficacy of treatment with CM-AT versus placebo for changes in the Aberrant Behavior Checklist subscale for Irritability/Agitation (ABC-I) between Baseline (defined as score at Screening Part 1 for efficacy assessments; in the event a subject has more than one Screening Part 1 value, the value to be used will be the last value of the variable measured prior to start of randomized treatment) and Week 12 visit and changes in the Aberrant Behavior Checklist subscale for Lethargy/Social Withdrawal (ABC-L) between Baseline and Week 12 of treatment.

To continue to monitor the safety of CM-AT in this population of children.

2. Study Design

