This is a Phase III, multi-center, randomized, double-blind, placebo-controlled study of approximately 300 subjects diagnosed with autism from approximately 35 clinical sites in the United States. Subjects will be between 3 and 8 years of age (inclusive) at the time of consent. All study participants must have an initial ABC-I score ≥ 11 and a diagnosis of Autistic Disorder as demonstrated by the Diagnostic and Statistical Manual for Mental Disorders IV Text Revision (DSM-IV-TR) and by the Autistic Diagnostic Interview − Revised (ADI-R). Subjects will also be screened using the Social Communication Questionnaire (SCQ) and must achieve a score ≥ 15 to be considered eligible.

After initial screening criteria are met, including the diagnosis of Autistic Disorder as demonstrated on the DSM-IV-TR, SCQ and ADI-R, the study participants will be administered the ABC. If their ABC-I score is greater than or equal to $11 (\geq 11)$ they can be enrolled and given a two-week initial blinded placebo run-in. At the end of the run-in, subjects will be evaluated and randomized if all inclusion criteria are satisfied.

The compliance and inclusion criteria required for randomization are: 1) subjects must take the study drug on the prescribed regimen and 2) continue to meet inclusion criteria. At the Visit 1 Visit, they will be reevaluated for their level of Irritability/Agitation with the ABC-I scale. If a subject's score on the ABC-I scale has increased or decreased by 30% or more, or is <9 on the retest, they will be discontinued from the study and not randomized. Qualified subjects can be randomized into the study if they meet all inclusion/exclusion criteria.

After enrolling in the study at a clinical site, subjects ultimately randomized to treatment will receive study drug or placebo three times daily with food for a

period of 12 weeks. Parents will keep a missed dose log. Subjects will be seen at Week 2, 4, 6, 8, 10, and 12, post-randomization. Standardized measures of behavior, health, and quality of life will be utilized. In addition, measures of overall health including growth and weight will be obtained.

Subjects will be randomized in a 1:1 ratio to CM-AT or Placebo (both biomarker negative (>12.6 U/g) and positive (≤12.6 U/g) will be included). Randomization will be based upon study drug vs placebo.

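### Optional small gain: the primary MMRM adjusts for the Screening Part 1 ABC-I only and leaves out the Visit 1 ABC-I taken before randomisation

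*SAP*

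**What the plan says.** SAP 8.6.1 fits an MMRM with treatment, study center, visit and treatment-by-visit, and adds one ABC-I covariate: "The model will also include Baseline ABC-I score as a covariate and subject will be a random effect". SAP sections 5 and 6.1 define Baseline for efficacy as the Screening Part 1 score. SAP section 1 has a fallback under which "the value to be used will be the last value of the variable measured prior to start of randomized treatment". It applies only when a child has more than one Screening Part 1 value, so it does not move Baseline to Visit 1.

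The protocol's Statistical Considerations give the same one-score model: "Included in the model will be the main effects of randomized treatment group, visit, baseline ABC irritability, study center and the treatment-by-visit interaction effect".

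The second score is described in both documents.

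- SAP section 2: "At the Visit 1 Visit, they will be reevaluated for their level of Irritability/Agitation with the ABC-I scale".
- Protocol, additional criteria for randomisation: "The subject must meet the following additional inclusion criteria upon returning for Visit 1/Baseline in order to be randomized". On retest, the "score on the ABC-I must have increased or decreased by less than 30"% and must also be at least 9.

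The SAP already uses the Visit 1 score elsewhere. Under the missing-data part of 8.6.1 it is a predictor in the multiple imputation and a possible carried-forward value in the LOCF analysis. The treatment-by-center check, like the primary model, has only one score: "Included in the ANOVA model will be main effects for treatment, investigative center and Baseline ABC-I and the treatment-by-center interaction effect".

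**The concern.** Baseline adjustment is in the primary model to remove between-child variation from the Week 12 comparison. A second measurement of the same scale, taken about two weeks later and closer to the start of randomised treatment, may predict Week 12 at least as well as the first. It is already in the database and precedes randomisation. Adjusting for it cannot bias the comparison, and it leaves the endpoint unchanged. Leaving it out gives up some precision for nothing.

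A point of definition comes with it. Because Baseline is Screening Part 1, the randomisation visit falls after Baseline, and SAP 8.2 lists it among the efficacy collection times. The SAP does not say whether the Visit 1 score is a row in the MMRM. Read literally, the ITT requirement for a *post-Baseline* ABC-I is met by every properly randomised child through Visit 1. The protocol also labels the randomisation visit *Visit 1/Baseline*, which does not match the SAP's definition.

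**Working it through.** **The plan's own figure.** Inputs from SAP 8.1: changes of -3.7 (SD 7.0) and -0.6 (SD 5.0), two-sided 0.05, 90% power, 1:1 allocation.

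- Difference 3.1; pooled SD = √((49 + 25)/2) = √37 = 6.083.
- n = 2 × 37 × (1.960 + 1.282)² / 3.1² = 80.9, so 81 per group by the normal approximation and 82 by the t distribution. Power at 82 is 90.0% (t).
- 82/0.85 = 96.5, so 97. 97/0.60 = 161.7, so 162.

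The stated 82/97/162 reproduces.

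**Assumptions for the gain.** None of these is in the documents: ABC-I mean 15-18, SD 8, correlations with Week 12 (r) of 0.4-0.65, and a Screening-to-Visit 1 test-retest correlation ρ.

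**What ρ fits the plan.** SAP section 3 expects 324 of 350 children to pass the run-in (92.6%). Simulated trivariate normal scores were rounded and limited to 0-45. The three ABC-I rules were then applied (Screening at least 11, Visit 1 at least 9, change under 30%). The share of children with Screening at least 11 who pass is 56-75% at ρ = 0.6-0.8, 92-94% at 0.94 and 98% at 0.97. So 0.94 fits if the ABC-I rules are the only losses. If compliance or other exclusions also remove children, ρ must be higher and the gain smaller.

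**Hand check at ρ = 0.94, before the run-in rules.**

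- Both scores predict Week 12 equally. Residual variance is 1 - r² with Screening alone and 1 - 2r²/(1 + ρ) with both. At r = 0.4: 0.8351/0.8400, a fall of 0.6%. At r = 0.65: 0.5644/0.5775, a fall of 2.3%.
- Screening adds nothing once Visit 1 is known. Residual variance is 1 - ρ²r² with Screening alone and 1 - r² with both. At r = 0.4: 0.8400/0.8586, a fall of 2.2%. At r = 0.65: 0.5775/0.6267, a fall of 7.8%.

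**With the rules applied.** Selection narrows the score range and trims these gains. Power comes from the noncentral t with n = 82 per arm, difference 3.1, the Week 12 minus Screening SD scaled to 6.083, and one degree of freedom lost per covariate. This is a complete-data Week 12 ANCOVA standing in for the MMRM. Screening-only power is 92-96%.

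| ρ | Pass the rules | Fall in residual variance, equal prediction | Fall in residual variance, Screening adds nothing |
|---|---|---|---|
| 0.94 | 92-94% | 0.4-1.8% (+0.1 to +0.4 points) | 1.6-6.3% (+0.3 to +1.3) |
| 0.97 | 98% | 0.3-1.1% (at most +0.2) | 1.0-3.8% (+0.2 to +0.9) |
| 0.6-0.8 | 56-75% | 0.8-5.8% (+0.2 to +1.4) | not used: retention does not fit the plan |

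A variance fall of c is worth 82c/(1 - c) evaluable children per arm. At ρ = 0.94, c = 0.4% gives 0.3, c = 1.8% gives 1.5 and c = 6.3% gives 5.5.

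**One slope for all visits.** Neither document has a baseline-by-visit term, so a covariate entered as a main effect has one slope shared by Weeks 2 to 12. The large-sample, complete-data limit of that model was taken at ρ = 0.94, mean 16.5, SD 8, and between-visit correlations falling from 0.88 to 0.68.

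| Visit 1 correlation with ABC-I, Week 2 to Week 12 | Shared slope | Week 12-specific slope |
|---|---|---|
| 0.75 fading to 0.40 | about 0% | 0.5-1.6% |
| 0.80 fading to 0.50 | 0.5-1.6% | 0.8-2.8% |
| flat | same as Week 12-specific | same as shared |

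**The case against.** The strongest reply is that nothing is broken. Adjusting for the score that is subtracted is standard practice, and the Screening-only model already exceeds 90% power under these assumptions. All of that stands, so this is an optional refinement.

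The second objection is that the size is not established. That also stands. No correlation is given, and wider assumptions (scores up to mean 20 and SD 9, correlations 0.5-0.95) give falls of 1-12%. One set of extreme cases, with Visit 1 predicting Week 12 much better than Screening does (0.70 against 0.60), gives 17-23%. Part of the upper end comes from test-retest values whose retention contradicts the SAP's 324/350. At 0.94, even a Visit 1 advantage of 0.05 needs a negative Screening coefficient (-0.19 to -0.08). Those figures should not be relied on.

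The third is that a single added main effect might gain nothing. The shared-slope check confirms this, and it is why the fix includes covariate-by-visit terms.

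A reader might infer that the primary analysis is biased, or that the trial is underpowered. Neither follows. Both scores precede randomisation, and the sample size was set on the raw change SD without credit for any covariate. A reader might also infer from the protocol's *Visit 1/Baseline* label that its baseline term is the Visit 1 score, with Screening the one omitted. The SAP fixes the term at Screening Part 1, so this is a label to reconcile. Under either reading, one of the two scores is missing from the model.

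**Conclusion.** The omission is real and the gain is small. The planned model is valid, prespecified and unbiased, and 82/97/162 needs no correction. In the case closest to the SAP's own retention plan (test-retest about 0.94), adding Visit 1 ABC-I lowers Week 12 residual variance by 0.4-1.8%, or +0.1 to +0.4 power points, if both scores predict Week 12 equally. The most favourable coherent case, where Screening adds nothing beyond Visit 1, gives about 6% and +1.3 points. These figures rest on assumed correlations, on complete data, and on a slope specific to Week 12. With a shared slope the gain can fall to about zero. The priority is the lowest: worth doing if the SAP is being edited anyway.

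**What to change.** - Keep Screening Part 1 ABC-I as the subtracted Baseline and as a covariate. Add Visit 1 ABC-I as a second covariate in SAP 8.6.1 and in the protocol's list of model terms.
- Include covariate-by-visit interactions for both scores. Over six visits this is 1 + 5 + 5 = 11 further parameters, of which only the two Week 12 slopes bear directly on the Week 12 contrast.
- State that Visit 1 ABC-I is a covariate only and not an outcome row in the MMRM. Say how a child randomised without that score would be handled.
- Use the same model for the imputed datasets and for the interim z statistic in SAP section 9. Add the Visit 1 main effect to the Week 12 treatment-by-center ANOVA.
- Settle the change before any unblinded interim look.
- Do the same for ABC-L if it is collected at Visit 1, as SAP 8.2 suggests.
- Reconcile the protocol's *Visit 1/Baseline* label with the SAP's Baseline, and change *post-Baseline* to *post-randomisation* in the ITT definitions.
- Before deciding whether CGI-S needs a similar term, reconcile the SAP section 6 table, which gives it a randomisation-visit Baseline, with SAP 8.6.3, which says it has none.

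The cost is wording in both documents and a few degrees of freedom. There are no new data, and the endpoint, the subtracted Baseline and the sample size do not change.

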Study Rationale:	Sponsor studies have demonstrated the clinical potential of CM-AT formulations in treating core and non-core autism symptoms in subjects with autism ages 3-8 with low fecal chymotrypsin (FCT) levels when dosed at a level of 900mg 3x daily.  This study will further quantify the changes in the target population as measured by standardized behavioral and quality of life tests, physiological measures, as well as characterize the efficacy and safety of the product. The study will further delineate the efficacy in a population that is biomarker negative (>12.6U/g of fecal chymotrypsin) who have autism.  The data from this study will help determine safety and efficacy of CM-AT in pediatric patients with autism of both biomarkers positive and negative.

	This study will be undertaken in children whose Aberrant Behavior Checklist: subscale for Irritability / Agitation (ABC-I) ≥11 is at Screening/Enrollment. This number represents those who fall above approximately 0.5 std deviations from the mean seen in the Sponsor's 00101 study.
Safety:	Fecal globin levels, the presence of occult blood, α 1 -antitrypsin, and weight loss will be used to monitor the safety and tolerability of CM-AT.
	
 
The presence of fecal globin may indicate bleeding in the large intestine, while a positive occult blood may indicate bleeding along the entire gastrointestinal tract.
 

	• An increase in α 1 -antitrypsin may signal an immunologic response of the colonic mucosa, leading to potential formation of colonic strictures.
	Weight loss may be indicative of malabsorption.
	
 
All of the above markers may be linked due to gastrointestinal irritation, but have not specifically been noted thus far in the Sponsor's experience with enzyme therapies.
 

	
 
Parental input at the standard visits, diary entries, and other assessments will also be used to monitor safety.
 

	
 
Of 468 children with autism given pancreatic enzymes in early Sponsor studies, and in the Phase III clinical studies (00101 & 00102), in which 180 were initially enrolled, and 140 continued into Open-Label, the drug appeared to be safe and well-tolerated with no related SAE experienced in either study the duration of which has been greater than 288 weeks. Primarily, AEs appeared to be GI in nature.
 

Rating Instruments:	ABC, SRS-2 (Preschool or School Age), PedsQL Inventory – Family Impact Module, CGI (S), CGI (I).

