Low-level FCT ITT: All randomized subjects with pathologically low levels of FCT (≤12.6 U/g) who received study drug and had at least one post-Baseline ABC-I assessment. Subjects are analyzed under the treatment to which they are randomized. This is the primary analysis population for efficacy.

Non-Low-Level FCT (FCT >12.6) ITT: All non-low-level (FCT >12.6 U/g) randomized subjects who received study drug and had at least one post-Baseline ABC-I assessment. Subjects are analyzed under the treatment to which they are randomized. This is an exploratory analysis population for efficacy.

All Randomized: All randomized subjects. This is an exploratory analysis population for efficacy. Subjects are analyzed under the treatment to which they are randomized.

Low-level FCT All Randomized Subjects: All randomized subjects with pathologically low levels of FCT (≤12.6 U/g). This is a population for use in a sensitivity analysis of efficacy. Subjects are analyzed under the treatment to which they are randomized.

Non-Low-Level FCT (FCT >12.6) All Randomized Subjects: All non-low-level (FCT >12.6 U/g) randomized subjects. Subjects are analyzed under the treatment to which they are randomized. This is an exploratory analysis population for efficacy.

Per-Protocol (PP): All ITT subjects who have completed a Week 12 visit and have a Week 12 ABC-I score. Subjects are analyzed under the treatment to which they are randomized. This is an exploratory analysis population for efficacy.

Low-Level FCT (FCT \leq 12.6) Per Protocol (PP): All low-level (FCT \leq 12.6 U/g) PP Subjects. Subjects are analyzed under the treatment to which they are randomized. This is an exploratory analysis population for efficacy.

Non-Low-Level FCT (FCT >12.6) PP: All non-low-level (FCT >12.6 U/g) PP Subjects. Subjects are analyzed under the treatment to which they are randomized. This is an exploratory analysis population for efficacy.

Run-in Analysis Set: All subjects receiving at least one dose of placebo during the placebo-run in phase. All subjects will be analyzed as one group.

Safety Analysis Set: All subjects receiving at least one dose of randomized treatment. Subjects are analyzed under the treatment received. This is a primary analysis set for safety.

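### The treatment-by-FCT-status interaction is planned as a Week 12 ANOVA, which on observed data makes the ITT, All Randomized and PP versions essentially one completer analysis; it fits better in the MMRM

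*SAP*

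**What the plan says.** SAP 8.6.1 compares treatments on ABC-I with an MMRM on available data. Its terms are treatment, center, visit, treatment-by-visit and Baseline ABC-I.

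The same section checks treatment-by-center interaction in a separate ANOVA on change from Baseline to Week 12: "Included in the ANOVA model will be main effects for treatment, investigative center and Baseline ABC-I and the treatment-by-center interaction effect". It sets the threshold ("A 0.10 level of significance will be used to assess the interaction") and says how to read the result: "A non-significant interaction or an interaction significant but only quantitative in nature will support the pooling of results across study centers". It then adds that, for the PP, ITT and All Randomized sets, "a treatment-by-low-level status interaction will be assessed in a similar manner as the treatment-by-study center interaction". The FCT-status model itself is not written out.

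SAP Section 3 defines PP as "All ITT subjects who have completed a Week 12 visit and have a Week 12 ABC-I score". ITT requires a dose of study drug and at least one post-Baseline ABC-I. All Randomized has no further condition.

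The missing-data text in 8.6.1 says that the analyses above it are repeated after multiple imputation, but the only model it names for the imputed datasets is the primary MMRM. LOCF is likewise tied to the MMRM.

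The protocol synopsis (Study Rationale) says the data will help determine "safety and efficacy of CM-AT in pediatric patients with autism of both biomarkers positive and negative". Its Statistical Considerations plan MMRMs for FCT ≤ 12.6, FCT > 12.6 and all randomized patients, and no interaction test.

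**The concern.** Separate MMRMs in the two FCT groups estimate an effect in each group but do not test whether the effects differ. The interaction in SAP 8.6.1 is the only planned analysis that does.

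The method it points to has one outcome per child and no visit term, so a child without a Week 12 ABC-I contributes nothing. Two things follow on observed data:

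- Naming three analysis sets gives no robustness check, because they hold essentially the same children.
- The comparison between FCT groups is valid only if having a Week 12 score depends on nothing beyond the terms in the ANOVA. The MMRM estimates being compared also allow it to depend on the child's earlier post-Baseline scores.

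At stake is how trustworthy a supportive, exploratory result on the biomarker is. The trial's success criterion is not involved.

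**Working it through.** **Inputs from SAP 3 and 8.1.** Change of −3.7 (SD 7.0) on CM-AT and −0.6 (SD 5.0) on placebo; 82 evaluable low-FCT children per arm for 90% power; 15% withdrawal; 60% low-FCT; 162 randomized per arm, 324 in total.

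**Assumptions not in the documents.** The SDs and the 15% withdrawal, given for low-FCT children, also hold in non-low children. The treatment effect is 3.1 in low and 0 in non-low children. Dropout timing and within-subject correlation are as stated below.

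**1. The plan's own figure.** Common SD = √((49 + 25)/2) = √37 = 6.083. The normal approximation gives n = 2 × (1.96 + 1.2816)² × 37 / 3.1² = 80.9, so 81. The noncentral t gives 89.7% power at 81 and 90.04% at 82, so 82 reproduces. Then 82/0.85 = 96.5, so 97; and 97/0.60 = 161.7, so 162 per arm.

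**2. Who enters the ANOVA.** An ITT child with a Week 12 score is, by definition, a PP child, so the ITT and PP versions use the same children. Any difference between the two tables could come only from center pooling, which SAP 8.2 repeats in each analysis set. All Randomized could add only a child who was never dosed but has a Week 12 score. In numbers, 324 × 0.85 = 275.4 children remain and 324 × 0.15 = 48.6 do not. If the last observed visit of those who withdraw is spread evenly over six possibilities (none, Weeks 2, 4, 6, 8, 10), then 48.6 × 5/6 = 40.5 of them have post-Baseline scores that the MMRM would use and the ANOVA discards.

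**3. What the change is worth in power.** Non-low children per arm: 162 − 97 = 65. With n per arm in an FCT group, the treatment difference has variance (49 + 25)/n = 74/n. So SE(interaction) = √(74/n_low + 74/n_nonlow), and power at two-sided 0.10 is Φ(3.1/SE − 1.645), the other tail being negligible.

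| Analysis | Effective share of randomized | SE | Power |
|---|---|---|---|
| Completer ANOVA | 85% (82.45 and 55.25 per arm) | 1.496 | 66.6% |
| MMRM, correlation 0.3 to 0.9, AR(1) or compound symmetry, dropout spread evenly | 85.2% to 95.5% | 1.494 to 1.411 | 66.7% to 71.0% |
| No missing data | 100% (97 and 65 per arm) | 1.379 | 72.7% |

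The gain is about 0 to 4.5 percentage points.

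**4. Bias.** With a true interaction of −3.10, two-visit checks with about 16% dropout related to earlier response gave completer estimates from −3.08 (weak dependence) to −2.86 (strong dependence). Likelihood estimates under the same kind of dropout were −3.08 to −3.11. The completer bias is therefore about 0.02 to 0.24 points, at most 0.24/1.50 = 0.16 of a standard error. The upper end needs a logistic slope near 0.2 per ABC-I point, an odds ratio of about exp(0.2 × 7) = 4 per 7-point SD. The likelihood estimate looks unbiased partly because the assumed dropout depends only on observed scores.

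**The case against.** The strongest objection is the multiple-imputation text. The interaction ANOVA is one of the analyses above it. If the repeat covers the ANOVA, children without a Week 12 score are kept in that sensitivity run, and ITT and All Randomized no longer collapse to PP there. This stands in part. It does not change the observed-data ANOVA, and because only the MMRM is named for the imputed datasets, the reader cannot tell which is meant. So the collapse can be asserted only for the observed-data analysis.

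A reader might also infer that a p-value above 0.10 would lead the sponsor to pool the FCT groups. The documents do not say so. The pooling sentence concerns study centers, results by FCT group and for all levels are produced whatever the interaction shows, and success rests on the low-FCT MMRM alone. What remains is that the phrase about a similar manner does not say whether the center rule carries over, and the SAP should.

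A third objection is that the protocol promises no formal comparison between FCT groups and labels the non-low and all-level analyses exploratory. That is correct, and it limits the weight of the point. It does not make the completer ANOVA the better choice once the interaction is to be tested. Leaving FCT status out of the all-level MMRMs does not bias a randomized comparison, so that omission is not a fault in itself.

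**Conclusion.** The point holds as a cheap improvement to a supportive, exploratory analysis. On observed data, the plan's only direct test of effect difference by FCT status is a completer analysis of about 275 of 324 children. Its ITT and PP versions use the same children, and its All Randomized version essentially the same. It discards earlier-visit data and makes a stronger missing-data assumption than the MMRM.

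Two stronger readings should be avoided:

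- **That the ANOVA is why the interaction is underpowered.** The 66.6% reflects the sample size. The fix moves it to 66.7–71.0%, and complete data would give only 72.7%.
- **That the completer result would be materially biased.** The bias depends on assumed response-related dropout and was at most 0.16 of a standard error in the cases examined.

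The figures rest on withdrawal and SDs stated for low-FCT children being applied to non-low children, and on assumed dropout timing, within-subject correlation and non-low effect. The primary low-FCT MMRM is unaffected. ABC-L is analyzed in a similar manner (SAP 8.6.2), so its interaction test has the same limit. Children with no baseline FCT cannot be classified (SAP 8.3) and so drop out of this test under any of these models.

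**What to change.** In SAP 8.6.1, for the ITT and All Randomized sets:

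- Test the interaction in the MMRM by adding FCT status, status-by-visit, treatment-by-status and treatment-by-status-by-visit.
- Report the Week 12 treatment difference in each FCT group, and the difference between them, with 95% confidence intervals.
- Label any retained Week 12 ANOVA as completers only, and say whether the multiple-imputation repeat applies to it.
- State that the center-pooling rule does not apply to FCT status, and that a non-significant interaction is not evidence of equal effect.

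The cost is SAP wording and a few lines of code. The downside is a few extra model terms in an exploratory analysis.
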